**A Mechanistic Perspective on Post-Activation Performance
Enhancement Responsiveness: A Randomized Controlled
Study of Acute Changes in Muscle Architecture, Contractile
Property Kinetics, and Muscle Excitability**

NCT06982937

18.05.2025

Objectives and endpoints.

The primary objective is to test whether a heavy conditioning activity (CA; one set of 2–3 repetitions at ~90% 1RM) produces post-activation performance enhancement (PAPE) in countermovement jump (CMJ) height compared with a control treadmill warm-up within the 4–12 min window after the intervention. The analysis does not assume *a priori* when the maximal effect occurs; instead, the minute of maximal between-group difference (denoted T^*) will be identified empirically. The primary endpoint is the change in CMJ height from baseline (ΔCMJ) at post-intervention time points (4, 6, 8, 10, 12 min). Secondary endpoints include the time-course of ΔCMJ within the experimental group (EXP), individual responder status at each time point, and the associations between neuromuscular phenotype—estimated as %MHC-I from tensiomyography (TMG)—and the magnitude, timing, and likelihood of response. Ultrasound (USG) morphology (muscle thickness, pennation angle, derived fascicle length) will be analysed in parallel to performance endpoints. Electromyography (EMG), where available, will be treated analogously to USG/TMG (see below).

Data handling and derived variables.

At each time point, CMJ height is the mean of three trials; ΔCMJ and percentage change (% ΔCMJ) will be computed relative to baseline. Individual response is classified using MDC. USG outcomes will be averaged across three images; fascicle length is calculated as thickness divided by the sine of pennation angle (degrees converted to radians). TMG-based %MHC-I is estimated from delay, contraction, and half-relaxation times using the published multivariable model; TMG amplitudes and time constants may also be expressed as Δ or % Δ . If EMG is collected, signals will be band-pass filtered, rectified, quantified with 50-ms RMS, normalized (to MVC or M-wave), and summarized over task-relevant phases; % Δ at 4–12 min is computed analogously. Values >3.5 SD from group-time means will be flagged; primary analyses include all data, with winsorized sensitivity checks reported only if inferences change. Missing data will be not imputed for the primary analysis; mixed-effects models accommodate missingness assuming MAR.

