Primary analysis and identification of the peak time (T^*).

The confirmatory analysis uses a RM-ANOVA with ΔCMJ as the outcome, Group (EXP vs CON), Time (time effect: 4, 6, 8, 10, 12 min), and Group \times Time. If the interaction is significant, we estimate adjusted between-group contrasts at each minute with Bonferroni correction across the five time points. T^* is defined as the minute showing the largest positive EXP–CON difference in estimated marginal means (EMMs) with the smallest p-value. We report the EMM difference at T^* (95% CI) and effect size (d’Cohen). Greenhouse–Geisser correction if needed.

Within-group time-course and kinetics.

To describe the temporal profile without prespecifying a target minute, we analyse ΔCMJ across time within EXP using a one-way repeated-measures ANOVA (or LMM if assumptions are violated), followed by Bonferroni-adjusted pairwise EMMs to locate the within-group peak. To characterise response timing at the individual level, we model time to first and time to peak response (4–12 min) using Kaplan–Meier curves with censoring at 12 min, compare strata by log-rank tests, and fit Cox proportional-hazards models to estimate hazard ratios (HR, 95% CI) and concordance (C-index). This kinetics framework provides an assumption-light estimate of when athletes typically express PAPE.

Responder analyses and discrimination.

Responder distributions (Positive/neutral/adverse) will be compared between EXP and CON at each minute using likelihood χ^2 test. For mechanistic discrimination at specific minutes (including T^* once identified), we fit logistic models with %MHC-I as a continuous predictor and report ORs (95% CI),

Nagelkerke R², AIC, Hosmer–Lemeshow calibration, and ROC-AUC with sensitivity, specificity, and Youden's J cut-offs. Moderation analysis also will be used with simple slope analysis.

Phenotype and morphology linkages (USG/TMG/EMG).

Associations between %MHC-I and Δ CMJ will be quantified at each minute using Pearson's r. USG variables (thickness, pennation angle, fascicle length) will be analysed with the same three lenses applied to performance: (i) within-EXP time-course (rmANOVA/LMM with Tukey), (ii) responder linkage at each minute (one-way ANOVA or robust alternative; Hedges' g for P vs X), and (iii) phenotype linkage (correlations and moderation models). TMG (e.g., Dm, Tc, Tr) and EMG (e.g., normalized RMS, median frequency) follow this identical framework to ensure coherence across modalities.

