Moderation and mediation (pre-specified).

All moderators and predictors will be mean-centered; multicollinearity is checked (VIF < 5). Primary moderation models test whether (a) baseline CMJ modifies the effect of %MHC-I on Δ CMJ and (b) baseline morphology (thickness, pennation angle, fascicle length) modifies the effect of baseline CMJ on Δ CMJ. Significant interactions will be decomposed with simple slopes at -1 SD, mean, and +1 SD, with 95% CIs via nonparametric bootstrap (1,000 resamples) and publication-ready interaction plots. Exploratory mediation tests whether acute morphological change (e.g., % Δ thickness at a given minute) transmits baseline morphology effects to % Δ CMJ; indirect, direct, and total effects will be estimated by bootstrap (5,000 resamples; bias-corrected CIs) and interpreted cautiously.

Assumptions, multiplicity, and robustness.

Model diagnostics include residual normality (Shapiro–Wilk), homoscedasticity (residual–fitted patterns, Breusch–Pagan), linearity, and independence by design. Sphericity is tested for rmANOVA (Mauchly) with Greenhouse–Geisser corrections as needed. If mechanistic variables are skewed, appropriate transformations (e.g., log for EMG amplitude) are considered; otherwise we rely on LMM robustness. Multiplicity is controlled via Holm across the five between-group contrasts, FDR for correlation families, and restraint in post-hoc testing; moderation/mediation will be estimation-focused with full interval reporting and are not used to redefine the primary inference.

Reporting, visualization, and software.

We report means \pm SD with 95% CIs; between-group effects as Hedges' g; within-subject effects as d_{nZ} ; ANOVA-style effects as η^2 ; logistic results as ORs with AUC; and survival results as HRs with concordance. Figures include EMM trajectories with 95% CIs, individual waterfall plots with MDC bands, ROC curves for %MHC-I, Kaplan–Meier curves for first/peak response, interaction plots for significant moderations, and path diagrams for supported mediations. Analyses will be performed in Jamovi 2.6 and STATISTICA 13.1.

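### The five between-group contrasts depend on a Group×Time test that cannot see a constant effect, and Group has no decision rule

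*Combined protocol and SAP*

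**What the plan says.** The section on objectives and endpoints frames the primary question as an effect on jump height "compared with a control treadmill warm-up within the 4–12 min window after the intervention", and adds that "the minute of maximal between-group difference (denoted T^*) will be identified empirically". The outcome is a change score: "The primary endpoint is the change in CMJ height from baseline (ΔCMJ) at post-intervention time points (4, 6, 8, 10, 12 min").

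The primary analysis section fits an RM-ANOVA to ΔCMJ with "Group (EXP vs CON), Time (time effect: 4, 6, 8, 10, 12 min") and their interaction. It then makes the minute-by-minute comparison conditional: "If the interaction is significant, we estimate adjusted between-group contrasts at each minute with Bonferroni correction across the five time points". The following sentence carries no condition, but it needs the p-values from those contrasts: "T^* is defined as the minute showing the largest positive EXP–CON difference in estimated marginal means (EMMs) with the smallest p-value". The responder section plans logistic models at particular minutes, "including T^* once identified".

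The section on assumptions and multiplicity mentions the same comparisons without the condition: "Multiplicity is controlled via Holm across the five between-group contrasts".

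The document does not state a significance level, the meaning of a significant Group effect, or what happens when the interaction is not significant.

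**The concern.** The objective asks whether there is an effect anywhere in the window. The precondition asks whether the effect differs between minutes. If Time included a baseline level and the outcome were raw jump height, a constant post-intervention effect would show up in Group×Time. Here baseline has been subtracted and dropped as a level, so a constant effect sits entirely in the Group term.

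Two things follow. First, the adjusted contrasts can be blocked when the effect is real and sustained. Second, if Group is significant and the interaction is not, the plan does not say whether PAPE has been shown, so that could be decided after the data are seen. The status of T^* is then also unclear, and with it the analyses planned at T^*.

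**Working it through.** **No figure to reproduce.** The documents give no sample size, alpha, SD, within-subject correlation or effect size. From the plan come the outcome (ΔCMJ), the two groups, the five post-intervention minutes, the condition on the interaction, and the adjustment over five contrasts. Assumed for illustration: n = 20 per group, SD of ΔCMJ σ = 1, compound symmetry with correlation ρ = 0.5 / 0.8, two-sided α = 5%, no missing data.

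**Step 1: what the interaction measures.** Let d_t be the EXP–CON difference in mean ΔCMJ at minute t, and d̄ the mean of the five. With equal groups:

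- SS(Group×Time) = (n/2) Σ(d_t − d̄)²
- noncentrality λ = (n/2) Σ(δ_t − δ̄)² / [σ²(1 − ρ)], where δ_t is the true difference; degrees of freedom are 4 and 4(2n − 2) = 152

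If δ_t = δ at every minute, every deviation is zero. Then λ = 0 and the test rejects at rate α for any δ and any n.

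**Step 2: noncentrality for four profiles** (n/2 = 10; divide by 0.5 / 0.2).

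| Profile, SD units at 4, 6, 8, 10, 12 min | Σ(δ_t − δ̄)² | λ | Interaction significant (noncentral F) |
|---|---|---|---|
| Constant: 0.8 throughout | 0 | 0 / 0 | 5.0% / 5.0% |
| Plateau: 0.4, 0.8, 0.8, 0.8, 0.6 | 0.128 | 2.56 / 6.4 | 20.6% / 48.5% |
| Peaked: 0.2, 0.6, 0.8, 0.6, 0.2 | 0.288 | 5.76 / 14.4 | 44.0% / 86.5% |
| Narrow: 0, 0.2, 0.8, 0.2, 0 | 0.432 | 8.64 / 21.6 | 62.8% / 97.1% |

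A linear drift from 0.7 to 0.9 SD has sum 0.025 and λ = 0.5 / 1.25, giving 7.5% / 11.9%. A drift from 0.6 to 1.0 SD has sum 0.1 and λ = 2 / 5, giving 16.7% / 38.5%.

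**Step 3: chance of a positive finding** (Monte Carlo, 40,000 trials per scenario; contrasts tested at α/5 = 1%; Holm gives the same chance of at least one rejection as Bonferroni).

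| Profile | Contrast, with condition | Contrast, no condition | Group test | Group or conditional contrast |
|---|---|---|---|---|
| Constant | 4.5% / 4.0% | 79.0% / 65.9% | 88.8% / 76.8% | 89.1% / 77.0% |
| Plateau | 17.6% / 31.9% | 71.4% / 60.1% | 76.9% / 63.0% | 79.0% / 65.7% |
| Peaked | 30.6% / 43.5% | 55.6% / 47.9% | 48.3% / 36.4% | 58.0% / 49.0% |
| Narrow | 36.2% / 43.4% | 44.7% / 43.9% | 15.7% / 12.5% | 42.1% / 43.8% |

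The Group column can be checked by hand. The variance of a participant's five-minute mean is (1 + 4ρ)/5 = 0.6 / 0.84. For the constant profile the noncentrality is 0.8 × √10 / √0.6 = 3.27, or 0.8 × √10 / √0.84 = 2.76, on 38 df. That gives 88.9% / 76.7%.

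**Step 4: sensitivity for a constant effect.**

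- The interaction is significant in 4.7–5.3% of trials for n = 10 to 60 per group and effects of 0.8–1.2 SD.
- At n = 60 and 0.8 SD, a positive contrast is found in 5.1% / 5.0% with the condition and 99.9% / 99.2% without. A larger trial does not help.
- If alpha were 0.01 or 0.10, the interaction would be significant in 1.0% / 1.2% or 10.0% / 10.2%.
- With AR(1) errors and Greenhouse–Geisser at n = 20, the contrast figures are 4.4% / 4.2% against 85.4% / 72.1%.

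**Step 5: is the condition needed for error control?** With no true effect, the unconditional adjusted contrasts give a false finding in either direction in 3.0–4.5% of trials, and a false positive-direction finding in 1.5–2.3%. The adjustment is sufficient without the condition.

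**The case against.** The strongest reply is that Group is itself a term of the confirmatory model, so its test is produced unconditionally. The interaction condition then limits only the search for where the effect lies. If a significant Group effect counts, the Group-or-conditional-contrast rule beats the unconditional contrasts for the constant, plateau and peaked profiles and trails only for the narrow peak. This stands as far as it goes: the drop to 4–5% is the loss in the contrasts, not in every test the model produces. But the plan never states that rule. With each part at 5%, its null error in either direction would be 5.1–5.8% under compound symmetry and up to 6.3% under AR(1), so it would need a small alpha adjustment.

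Three further points are fair:

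- An exactly constant effect is a limiting case, and the plan expects a peak. The plateau and drift results show, however, that the loss extends to nearly flat profiles.
- The alpha-rate result needs sphericity or the Greenhouse–Geisser correction, which the plan applies where needed. Under AR(1) with correlation 0.8 the uncorrected test rejects in 7.6–7.8% of trials and the corrected test in 4.7–5.0%.
- The plan also promises plots of the estimated group means over time, and the multiplicity section names the contrasts without a condition. Neither lifts the explicit condition in the primary analysis section or supplies a decision rule.

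**Conclusion.** The concern holds, with high confidence, and should be fixed. The stated rule directs the contrasts for the primary objective through a test of a different hypothesis, and no sentence covers the case of a null interaction. That a constant effect passes only at the alpha rate is algebra and does not depend on sample size, SD or effect size.

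The practical loss in this trial is unknown, because every power figure rests on assumed inputs. Under them, the loss in the chance of a positive contrast at ρ = 0.5 / 0.8 runs from 79.0 − 4.5 = 74.5 / 65.9 − 4.0 = 61.9 percentage points for a constant effect to 44.7 − 36.2 = 8.5 / 43.9 − 43.4 = 0.5 points for a narrow peak. With AR(1) errors and Greenhouse–Geisser, the narrow peak at correlation 0.8 gives 37.6% against 43.8%.

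**What to change.** In the primary analysis section:

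1. Remove the condition on the interaction. Always estimate the five EXP–CON contrasts in ΔCMJ, as the test of the primary objective, under one named multiplicity adjustment. The plan now names Bonferroni in one place and Holm in another; that mismatch is a separate point, but the same edit can settle it.
2. State alpha and the rule: PAPE within 4–12 min is concluded if at least one adjusted contrast is significant and positive, at a two-sided familywise 5%.
3. Use Group×Time only to describe whether the effect varies over the window.
4. Report the Group effect (mean ΔCMJ difference over 4–12 min, with 95% CI) as supportive.

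T^* then always has the estimates and p-values that its definition needs.

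A written decision rule for Group would also close the gap. Its drawbacks are that Group alone has only 15.7% / 12.5% power for the narrow peak, and that Group combined with the conditional contrasts needs the alpha adjustment noted above.

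The cost is wording only, with no extra data or software. The one downside is power for a constant effect: 79.0% / 65.9% with the contrasts against 88.8% / 76.8% with the Group test, about 10 percentage points, under the assumed inputs.

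### Cheap improvement, not an error: a max-t adjustment of the five EXP–CON contrasts would use the correlation from their shared baseline, which Bonferroni and Holm leave unused

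*Combined protocol and SAP*

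**What the plan says.** Under *Data handling and derived variables*, "ΔCMJ and percentage change (% ΔCMJ) will be computed relative to baseline". There is one baseline, and it enters all five post-intervention changes (4, 6, 8, 10 and 12 min).

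Under *Primary analysis and identification of the peak time (T\*)*, "The confirmatory analysis uses a RM-ANOVA with ΔCMJ as the outcome", with Group, Time and their interaction. The contrasts are a conditional second step, reached only after a significant interaction: "we estimate adjusted between-group contrasts at each minute with Bonferroni correction across the five time points". T* is then chosen from the five minutes, and the section adds: "We report the EMM difference at T^* (95% CI) and effect size". It does not say whether that interval is adjusted for the choice among five minutes.

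Under *Assumptions, multiplicity, and robustness*, the adjustment for the same family is different: "Multiplicity is controlled via Holm across the five between-group contrasts".

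The document states no alpha, sidedness, sample size, allocation ratio, SD, target power or correlation among the five changes.

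**The concern.** Each athlete's five ΔCMJ values contain the same baseline measurement. An unusually low or high baseline moves all five together, so the five EXP–CON differences tend to rise and fall together. Bonferroni and the first step of Holm both compare the smallest p-value with alpha/5, whatever that correlation is.

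These contrasts matter for the main claim. A significant interaction shows only that the group difference changes over time. It does not show that EXP exceeds CON at any minute. The contrasts supply that answer, and T* with it. If their threshold is stricter than familywise control requires, a real effect at the best minute is missed somewhat more often than it need be. Because the two sections name different adjustments, this wording has to be revisited in any case.

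**Working it through.** The plan gives no figure to reproduce. Assumptions: two-sided familywise alpha of 0.05, 1:1 allocation, 15 or 20 athletes per arm, normal ΔCMJ with one common correlation ρ across minutes, and effects in SD units of ΔCMJ.

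**Step 1: correlation from the shared baseline.** Let the six raw measures have variance σ² and common correlation r.
- Cov(Yj − Y0, Yk − Y0) = σ²(r − r − r + 1) = σ²(1 − r).
- Var(Yj − Y0) = 2σ²(1 − r).
- The ratio is ρ = 0.5.

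Departures go both ways. Let B be the baseline error variance, P the minute-specific post variance and S the variance of a stable athlete difference in response.
- Larger post variance: ρ = B/(B + P). With P = 2B, ρ = 1/3 = 0.33.
- Stable differences in response, with P = B: ρ = (B + S)/(2B + S). Reaching 0.7 needs S = 1.33B (2.33/3.33); reaching 0.85 needs S = 4.67B (5.67/6.67).

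**Step 2: threshold.** Bonferroni gives 0.05/5 = 0.01 per contrast. Holm tests the smallest p-value at the same 0.01. The chance of at least one rejection is therefore identical under both; they can differ only for the remaining minutes.

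**Step 3: familywise error of the contrast step by itself, all five nulls true (simulated).**

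| ρ | Familywise error, 15–20 per arm | Critical abs(t) at 15 per arm: Bonferroni | max-t |
|---|---|---|---|
| 0.5 | about 4.2% | 2.76 | 2.69 |
| 0.7 | about 3.5% | 2.76 | 2.60–2.62 |
| 0.85 | about 2.7% | 2.76 | 2.46–2.48 |

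Large-sample values agree: 4.67% at ρ = 0.3, 4.19% at 0.5, 3.48% at 0.7 and 2.32% at 0.9. With unrelated contrasts it would be 1 − 0.99⁵ = 4.90%. It never exceeds 5%.

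Simultaneous intervals shrink in proportion to the critical value: 2.69/2.76 = 0.97 at ρ = 0.5, 2.62/2.76 = 0.95 at 0.7 and about 2.48/2.76 = 0.90 at 0.85.

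**Step 4: the interaction test.** Its simulated size under the null is 4.8–5.2%. The adjustment of the contrasts does not enter it.

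**Step 5: power of the plan as written.** This is the probability of a significant interaction and at least one significant contrast, Bonferroni → max-t.

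| Effect at 4/6/8/10/12 min (SD) | Per arm | ρ = 0.5 | ρ = 0.7 | ρ = 0.85 |
|---|---|---|---|---|
| 0.2/0.5/0.8/0.5/0.2 | 15 | 17.1→18.1% | 21.3→24.2% | 27.0→35.7% |
| 0.2/0.5/0.8/0.5/0.2 | 20 | 26.2→27.4% | 33.9→37.4% | 42.8→52.6% |
| 0.4/0.7/0.9/0.7/0.4 | 15 | 16.2→16.8% | 21.7→23.9% | 31.9→38.6% |
| 0.8 throughout | 15 | 4.4→4.5% | 3.7→4.0% | 3.2→3.7% |

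The peaked rows gain 0.6–1.2, 2.2–3.5 and 6.7–9.8 points. Over the peaked settings examined, the ranges are about 1–2, 2–6 and 7–11 points. A flatter profile (0.5/0.7/0.8/0.7/0.5 SD, 15 per arm) gains only 0.2, 0.9 and 2.9 points.

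**The case against.** The strongest reply is that nothing here is wrong. Bonferroni and Holm give strong familywise control without estimating a 5 × 5 correlation matrix, they need no extra software, and some adjustment is required because T* is picked from five minutes. Mild conservatism is an accepted price. That stands, and it is why this is an improvement rather than an error.

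A reader might infer more than the documents support:

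- **That the confirmatory test runs below 5%.** The plan gives the confirmatory role to the RM-ANOVA, whose level the adjustment does not touch.
- **That the two methods treat the contrasts as independent.** Both hold under any dependence; they simply do not use it. The plan nowhere claims independence.
- **That the contrasts are strongly correlated.** No correlation is given. Only 0.5 has a basis in the design, and only under the equal-variance, equal-correlation condition. At about 0.3 the loss is negligible.
- **That power is thrown away for nothing.** The adjustment buys needed protection. The narrower statement is that max-t gives the same familywise control with a lower critical value.
- **That power rises by 6–7 points at correlation 0.7 and 9–11 at 0.85 whatever the effect looks like.** Such figures come from the contrasts without the interaction gate. For an effect constant over time the gate itself removes the power: at 15 per arm, ungated Bonferroni contrasts detect it in roughly 48–65% of trials against 3–4% with the gate. Changing the adjustment does not repair that.

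A practical objection also stands in part. The plan expects missing data and relies on mixed models under MAR, while a label permutation needs a rule for athletes with missing minutes. The multivariate-t version, applied to mixed-model contrasts, avoids this.

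**Conclusion.** The contrasts that identify T* and carry the EXP–CON claim are valid but somewhat conservative. The size rests entirely on assumed values of alpha, sample size and correlation. At 0.5, the value with a design basis, the loss is small: familywise error of about 4.2% instead of 5%, and 1–2 points of power for a peaked effect. It becomes material only if athletes differ stably in their response by enough to push the correlation towards 0.85, and only if the effect is peaked. For a constant effect the gain is close to zero. The priority is low, but the change is cheap and would settle the Bonferroni/Holm conflict at the same time.

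**What to change.** In both sections, replace the Bonferroni and Holm statements with one rule for the five contrasts: a step-down max-t adjustment at a stated two-sided familywise alpha. Choose one form in advance:

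- **Permutation.** Permute EXP/CON labels across athletes, keep each athlete's five ΔCMJ values together, and refer the absolute t statistics to the permutation distribution of their maximum. State how athletes with missing minutes are handled.
- **Multivariate t.** Apply it to the EMM contrasts from the mixed model, which also accommodates incomplete athletes.

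Use the single-step critical value of the same method for simultaneous 95% intervals at all five minutes. The interval at T* is then covered for the choice among minutes.

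Cost: a few sentences in the SAP, a short script outside the named Jamovi and STATISTICA packages, and slightly more complex reporting. Data collection does not change. If the sponsor prefers to stay within the named software, naming Holm alone in both sections would be valid and would remove the conflict, but it would leave the efficiency gain and the interval at T* unaddressed.

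### T* is picked by ranking after a non-directional interaction test, with no requirement that the contrast at T* be significant and no rule for when no minute qualifies

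*Combined protocol and SAP*

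**What the plan says.** The primary objective (Objectives and endpoints) is directional: whether the conditioning activity "produces post-activation performance enhancement (PAPE) in countermovement jump (CMJ) height compared with a control treadmill warm-up within the 4–12 min window". The endpoint is the "change in CMJ height from baseline (ΔCMJ) at post-intervention time points (4, 6, 8, 10, 12 min". That section adds that "the minute of maximal between-group difference (denoted T^*) will be identified empirically".

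The operative rule is under Primary analysis and identification of the peak time:

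- Model: "The confirmatory analysis uses a RM-ANOVA with ΔCMJ as the outcome", with Group, Time and their interaction.
- Gate: "If the interaction is significant, we estimate adjusted between-group contrasts at each minute with Bonferroni correction across the five time points".
- Selection: T* is "defined as the minute showing the largest positive EXP–CON difference in estimated marginal means (EMMs", followed by "with the smallest p-value".
- Output: the difference at T* with a 95% CI (not said to be adjusted) and an effect size.

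Under Responder analyses and discrimination, the %MHC-I logistic models are fitted at particular minutes, T* among them. Under Assumptions, multiplicity, and robustness, the five contrasts are controlled by Holm, whereas the primary analysis section says Bonferroni.

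No section requires the contrast at T* to be significant after adjustment or its interval to exclude zero. None says what is reported if no minute meets the definition, or which result counts as showing PAPE.

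**The concern.** A Group × Time test detects any departure from parallel profiles. It responds to benefit that appears later, and equally to an early loss in EXP that wears off. Once it is significant, the selection step looks for the best-looking positive minute. If the true differences at the later minutes are zero, one of them will often be positive by chance, and nothing in the rule stops it from being labelled T*.

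The question the trial asks is whether EXP jumps higher than CON. A peak minute with a positive difference and an effect size invites the answer yes, even where the only real effect ran the other way. The same minute then enters the T*-specific logistic and ROC models, with ORs and Youden cut-offs for %MHC-I.

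**Working it through.** **Inputs.** From the documents: two groups, five minutes, the interaction gate, Greenhouse–Geisser correction if needed, Bonferroni across five contrasts, and the two-part T* definition. Not given, so assumed: two-sided alpha 0.05, equal arms of 10–30, equal correlation between minutes of 0.6–0.8, and the true EXP–CON profile in SD units. The plan states no figure on this point to reproduce.

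**Step 1: the gate can open with no benefit.** Take true differences of −1, 0, 0, 0, 0 SD at 4, 6, 8, 10 and 12 min. Their mean is −1/5 = −0.2. Deviations from it are −0.8 once and +0.2 four times, with sum of squares 0.64 + 4 × 0.04 = 0.80. The interaction is real, yet no minute has a positive true difference.

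**Step 2: a positive minute is then easy to find.** For the four null minutes, the chance that at least one observed difference is positive is 1 − 0.5⁴ = 94% if they were independent and 50% if perfectly correlated. Before conditioning on a significant interaction, correlated minutes lie between these values.

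**Step 3: simulation of the written rule.** With n per arm, the difference at minute j is d_j = mean(EXP) − mean(CON) and t_j = d_j / (s_j √(2/n)). The Bonferroni threshold is 0.05/5 = 0.01. The gate is the Greenhouse–Geisser-corrected interaction F-test at 0.05. The definition was read in two ways:

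- Reading A: the largest positive d_j decides. Ranking p among positive minutes only names a T* equally often.
- Reading B: that minute must also have the smallest p of all five.

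True loss of 0.75 or 1 SD at 4 min, zero elsewhere:

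| Quantity | Result |
|---|---|
| Interaction significant, −1 SD | 63–100% of trials |
| Interaction significant, −0.75 SD | 36–100% of trials |
| T* named, reading A | about 68–83% of interaction-significant trials |
| T* named, reading B | about 2–21% of the same trials |
| Unadjusted p<0.05 at the largest positive minute | about 5–12% of the same trials |
| Bonferroni-significant positive contrast there | about 1–3% of the same trials |

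No minute qualifies in the remaining 17–32% (100 − 83, 100 − 68) under A, or 79–98% (100 − 21, 100 − 2) under B. The plan is silent on both.

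**Step 4: a different profile.** A second simulation used −0.8, −0.4, 0, 0, 0 SD, correlation 0.5–0.85 and an uncorrected F-test. The interaction was significant in 39–100% of trials and T* was named under reading A in 33–69% of all trials. Of those, 97–98% had no Bonferroni-significant positive contrast. In 66–92% of them the smallest p belonged to a negative contrast, so reading B would keep at most 8–34%.

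Example with 20 per arm and correlation 0.7:

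- Interaction significant: 92.1% of trials.
- T* named under A: 64.6%.
- T* named under B: at most 64.6% × (1 − 0.824) = 11.4%.
- T* named with a Bonferroni-significant positive contrast: 1.2%.

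With EXP truly worse at every minute (−0.8, −0.4, −0.1, −0.1, −0.1), reading A still named T* in 23–52% of trials.

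**The case against.** **The p-value clause is part of the rule.** It cannot be set aside because it lacks a threshold. Read strictly, it often blocks a T* in exactly this scenario, since the smallest p usually belongs to the early loss. This stands, so 68–83% cannot be quoted alone as the rate at which T* is named. But the plan does not say which reading applies, and the strict one still demands no significance.

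**T* is not a verdict.** A reader might infer that naming T* amounts to declaring PAPE. The documents do not say so; Objectives and endpoints describes T* neutrally as the minute of maximal difference. Equally, nothing else in the plan says what would establish PAPE.

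**The evidence is on view.** Adjusted contrasts at every minute, a 95% CI at T* and trajectories with intervals are all to be reported. This stands: the interval would seldom lie above zero.

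**Downstream reach is limited.** The logistic models are not confined to T*, the %MHC-I correlations run at every minute, and these serve secondary endpoints. This stands as well.

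**The plan does not forecast a mean loss.** It says "Responder distributions (Positive/neutral/adverse) will be compared between EXP and CON at each minute", and one might infer that impairment in EXP is expected. That is an individual classification based on MDC and applied to both arms; it predicts nothing about the group mean. The loss used above is an assumption.

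**A T* does not exist in every trial.** The short description in the objectives might suggest so, but the operative rule has a gate and a sign requirement. With no effect at all, T* is named in only about 4–5% of trials.

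**Conclusion.** The gap is real and follows from the wording alone: a non-directional gate, a selection by rank, no significance condition, and no instruction for when nothing qualifies. Its frequency rests on assumed sample size, correlation, alpha and effect profile, and on how the p-value clause is read. The fair statement of size is therefore the pair of ranges, about 68–83% and about 2–21% of interaction-significant trials, against about 1–3% with an adjusted-significant positive contrast.

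The stronger conclusion, that the plan would declare an enhancement never shown, goes beyond the text. The reported contrasts and interval would usually reveal the weakness. What remains is a misleading label and T*-specific models built on a minute that may be noise. This should be fixed before analysis; it does not by itself invalidate the primary comparison.

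**What to change.** Add to the primary analysis section, in substance:

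> *PAPE is concluded, and T\* is named, only if at least one minute has a positive EXP–CON difference with multiplicity-adjusted p<0.05. T\* is the minute with the largest difference among those. Otherwise the result is reported as PAPE not demonstrated, the largest difference is given descriptively, and T\*-specific models are not run; other by-minute analyses stand. Significant negative contrasts are reported as impairment.*

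This replaces the present two-part definition, so the ambiguity over the p-value clause goes with it. Name one adjustment in both places where the plan now says Bonferroni and Holm.

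In the −0.8, −0.4, 0, 0, 0 SD scenario, requiring a Bonferroni-significant positive contrast cuts naming under reading A from 33–69% of trials to about 0.9–1.4%; Holm gives practically the same. With no effect at any minute it falls from about 4–5% to 0.1–0.5%.

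The cost is a few sentences and no new data. The downside is that no T* can be quoted when no benefit is shown.
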